Title : Remifentanil-Sparing E\_ect of Pectoral Nerve Block Type II in Breast Surgery under Surgical Pleth Index-Guided Analgesia during Total Intravenous Anesthesia

NCT number : NCT03210220

Document date : June 16, 2019

The ethics committee of Gachon University Gil Hospital approved this study. The study was registered at www.ClinicalTrials.gov (NCT03210220) prior to patient recruitment. Written informed consent was provided by all participants.

The inclusion criteria for this study were the following: women, aged between 20 and 65 years, with an American Society of Anesthesiologists physical status of 1 or 2, who were scheduled for BCS with SLNB for the treatment of breast cancer. The exclusion criteria were as follows: patients receiving anticoagulant therapy, those with bleeding disorders, hypersensitivity to local anesthetics, body mass index greater than 35 kg/m2, the presence of spine or chest wall deformities, and pregnancy. Patients either received the Pecs II block (Pecs group) or did not receive it (control group). One anesthesiologist ([name]) performed all blocks in the Pecs group enrolled patients. After the intervention, the participants and the investigator responsible for the study outcome assessment were blinded.

Premedication was not given. Electrocardiography, non-invasive blood pressure monitoring and the bispectral index (BIS vista monitor revision 3.0; Aspect Medical Systems, Norwood, MA, USA) were applied in the operating room. SPI (S5 monitor; GE Healthcare, Helsinki, Finland) was monitored using a pulse oximeter sensor attached to the index finger contralateral to the operative site. For anesthesia induction and maintenance, lidocaine (1 mg/kg), propofol, and remifentanil were administered. The effect-site concentrations of propofol and remifentanil were automatically calculated by Schnider's [15] and Minto's [16] pharmacokinetic models, respectively, using a target-controlled infusion (TCI) pump (Orchestra; Fresenius Kabi, Bad Homburg, Germany). To facilitate orotracheal intubation, rocuronium (0.8 mg/kg) was administered after loss of consciousness.

For the patients in the Pecs group, a linear ultrasound probe was placed on the lateral third of the clavicle with bilateral abduction in the supine position. After identifying the axillary vein and artery, the ultrasound probe was positioned inferio-laterally, between the 3rd and 4th ribs, and then the pectoralis major and minor, and serratus anterior muscles were confirmed. The needle was advanced in a medio-lateral direction in-plane view of the ultrasound. For the Pecs II block, a total 30 mL of 0.5% ropivacaine was injected. First, the needle tip was advanced into the fascia between the pectoralis major and minor muscles and 10 mL of 0.5% ropivacaine was injected. Thereafter, the needle tip was advanced into the tissue plane between the pectoralis minor and serratus anterior muscles, and 20 mL of 0.5% ropivacaine was injected in a similar manner.

Fifteen minutes after the Pecs II block, a skin incision was made for the scheduled surgery. During

the surgery, the remifentanil dose was adjusted to a target SPI of 20–50 and the propofol dose was adjusted to a target BIS of 40–60, using a TCI pump. When the SPI was >50 or <20, the remifentanile effect-site concentration was adjusted to a step of 0.5 ng/kg with intervals of 1 min or more. When the BIS value was >60 or <40, the propofol effect-site concentration was adjusted to a step of 0.5 g/kg with intervals of 1 min or more. When the systolic blood pressure dropped below 90 mm Hg or below 80% of the baseline value, ephedrine 5 mg was administered intravenously at 2-min intervals. If the heart rate (HR) dropped below 50 beats/min, atropine 0.5 mg was administered intravenously.

Patient-controlled analgesia (PCA) (Accufuser plus®, Wooyoung medical, Seoul, Korea) was provided for 48 h with ketorolac 120 mg and sufentanil 50 g in normal saline 100 mL, (basal infusion rate 2 mL/h, 0.5 mL intermittent bolus with a 15 min lock-out interval). For preventing PONV, ramosetron 0.3 mg was administered intravenously before the end of the surgery.

In the postanesthetic care unit (PACU), the postoperative pain was evaluated using an 11-point numerical rating scale (NRS) (0–10) and was accessed immediately after arrival at the PACU, 1 h postoperatively, 16–24 h postoperatively, and 24–48 h postoperatively. Fentanyl 50 g bolus was administered as a rescue analgesic agent when the NRS was greater than 5 points.

The primary outcome was the intraoperative remifentanil consumption, and the secondary outcomes were the postoperative pain score and rescue analgesic requirement. The sample size was calculated based on the previous study of breast cancer surgery under TIVA. The intraoperative remifentanil consumption was 10.9 2.9 g/kg/h and 7.3 3.3 g/kg/h in the control and Pecs groups, respectively. With type 1 error of 0.05 and a power of 0.9, the study required 14 patients in each group. Considering the possible drop-out, 20 patients were included in each group. Patients were randomly assigned to the Pecs group (n = 20) or the control group (n = 20), based on a randomized list generated with Excel 2013 (Microsoft office, Redmond, WA, USA), without stratification.

Data were analyzed using SPSS 19.0 (SPSS, Chicago, IL, USA). Values were presented as number of patients, medians (interquartile ranges; IQR) or mean standard deviation (SD). The Kolmogorov-Smirnov test was performed for the normality test of continuous variables. The normally distributed data were presented as mean SD and the skewed data were presented as median (IQR). An independent t-test was used for normally distributed variables (intraoperative dosages of remifentanil and propofol), and the Mann–Whitney U Test was used for variables with a non-normal distribution (postoperative pain scores). The chi-squared test or Fisher's exact test was

used to analyze the categorical data (the use of atropine, ephedrine and rescue analgesics), where appropriate. Repeated, measured ANOVA was used for accessing the intergroup differences of MBP, HR, SPI, and BIS over time. Statistical significance was accepted for p value < 0.05.

Primary completion date : December 30, 2018

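### The blinding statement leaves out whoever titrates remifentanil, whose target changes make up the primary outcome; the SPI rule limits arm-linked discretion but does not remove it

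*Combined protocol and SAP*

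**What the plan says.** The sections of the combined protocol and SAP are unnumbered.

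- **Groups and blinding (eligibility paragraph).** Controls do not receive the block; no sham, dressing or screen is described. One anesthesiologist "performed all blocks in the Pecs group enrolled patients". Of blinding the plan says: "After the intervention, the participants and the investigator responsible for the study outcome assessment were blinded". Nobody else is named as blinded.
- **Timing (intraoperative management).** "Fifteen minutes after the Pecs II block, a skin incision was made for the scheduled surgery". No matching wait is described for controls.
- **Titration (intraoperative management).** During surgery "the remifentanil dose was adjusted to a target SPI of 20–50". When SPI is above 50 or below 20, "the remifentanile effect-site concentration was adjusted to a step of 0.5 ng/kg with intervals of 1 min or more". No starting target is given, and no upper limit on the time to respond.
- **Outcome (outcomes and sample size).** "The primary outcome was the intraoperative remifentanil consumption", compared by an independent t-test.
- **Related analysis (statistical analysis).** A repeated-measures ANOVA compares SPI, among other monitored variables, between the groups over time.

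**The concern.** Remifentanil consumption is not observed passively. It is the accumulated result of targets that a person sets. If that person knows the arm and expects sparing, which the trial's title announces, the expectation can enter the outcome while the drug is being given. Blinding the assessor protects the pain scores, but it cannot correct a dose already delivered. Blinding the participants adds little, because they are anesthetized during titration. Randomization balances the patients, not their later handling.

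The SPI band and fixed step are a real restraint. What they leave open is the starting target and the speed of response. Stepping up promptly and down late in controls, and the reverse in the Pecs group, would raise the consumption difference. The t-test on consumption alone cannot tell that from a block effect. Delays unrelated to arm add no bias.

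**Working it through.** **1. The plan's own figures.** Planning values are 10.9 (SD 2.9) and 7.3 (SD 3.3) µg/kg/h, so the difference is 10.9 − 7.3 = 3.6. The pooled SD is √((2.9² + 3.3²)/2) = 3.106. With two-sided α 0.05 (sidedness is not stated) and power 0.90, n = 2(1.960 + 1.282)² × SD²/3.6². This gives 13.6, so 14 per group, with SD 2.9, and 15.6, so 16, with the pooled SD. The stated 14 reproduces and is not in dispute.

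**2. What size of bias matters with 20 per group.** The standard error is 3.106 × √(2/20) = 0.982. An observed difference of 2.024 × 0.982 = 1.99 reaches p<0.05. If the true effect is zero and titration alone shifts the difference by b, the t-test has noncentrality b/0.982. Shifts of 5%, 10%, 15% and 20% of the control mean (0.55, 1.09, 1.64 and 2.18) give rejection in about 8%, 19%, 37% and 58% of trials.

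**3. What shift the rule could allow.** The documents give no SPI dynamics, so every input here is assumed.

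- SPI = 35 + s × (need + phase − Ce) + autocorrelated noise (ρ 0.8), limited to 0–100, over 90 minutes. Ce is the remifentanil effect-site concentration.
- Ce rises 0.5 when SPI >50 and falls 0.5 when SPI <20. The step is read as ng/mL. Up and down steps have separate check intervals.
- s = 5, 8 or 12 points per ng/mL; noise SD 5 or 8; surgical phase swing 0, 1 or 1.5 ng/mL; start 3, 4 or 5 ng/mL. That makes 3 × 2 × 3 × 3 = 54 input sets.
- Consumption = 2.2 × mean Ce. Patient need is tuned so that the null arm has mean about 9.1 (midpoint of 10.9 and 7.3) and SD about 3.1.

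Results with no true effect, 20 per group, median (range) over the 54 sets:

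| Titrator behavior | False difference, µg/kg/h | Median share of 3.6 | p<0.05 |
|---|---|---|---|
| (a) Controls start 1 ng/mL higher | 0.25 (0.08–0.78) | 7% | 6% (5–13%) |
| (b) Step-down at 3 min in controls only | 0.40 (0.05–1.00) | 11% | 7% (4–19%) |
| (c) Up at 1 and down at 3 min in controls, the reverse in Pecs | 0.78 (0.30–1.72) | 22% | 13% (6–47%) |
| (d) As (c), with 5 min | 1.29 (0.49–2.48) | 36% | 29% (7–84%) |
| (e) As (c), in half the patients | 0.39 (0.20–0.83) | 11% | 7% (5–14%) |
| Blinded titrator, free starts (±1 ng/mL) and intervals of 1–5 min | 0.00 (−0.09 to 0.07) | 0% | 5% (4–6%) |

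The formula in step 2, applied to the medians 0.25, 0.40, 0.78 and 1.29, gives noncentralities 0.25, 0.41, 0.79 and 1.31 and rejection of 6%, 7%, 12% and 25%, close to the simulated 6%, 7%, 13% and 29%. Separately coded versions of the model gave 0.80–0.82 for (c) and 1.30–1.32 for (d).

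**4. Would the planned SPI comparison show it?** Late step-up in Pecs and late step-down in controls leave SPI higher in Pecs. Mean SPI was compared between arms in simulated trials of the same kind, with a t-test standing in for the ANOVA group effect.

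| | Consumption p<0.05 | SPI p<0.05 | Consumption p<0.05 without an SPI signal |
|---|---|---|---|
| (c) | 14% | 86% (9–100%) | 5% (0–18%) |
| (d) | 30% | 99% (14–100%) | 1% (0–25%) |

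The medians favor detection, but the lower ends of 9% and 14% show input sets in which it would usually be missed.

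**The case against.** **The plan already has a relevant check.** The between-arm SPI analysis should expose the larger scenarios, and in most input sets it does so more often than they produce a false positive. This largely stands. But the comparison detects bias and does not remove it, it is weak in some sets, and nothing in the plan ties its result to the reading of consumption. The detection figures also assume no true block effect.

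**Long delays may not comply with the rule.** The adjustment is due when SPI leaves the band, and the one-minute interval most naturally governs spacing between successive steps. On that reading, leaving SPI above 50 for 3–5 minutes conflicts with the target. This is a fair reading and weakens (b) to (e). The text still sets only a minimum interval, and the starting target stays open on either reading.

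**Material bias needs near-systematic conduct.** This stands. Cases (a), (b) and (e) have median rejection of 6–7% against a nominal 5%. Only (c) and (d) move it materially, and they require opposite delays, in both directions, in every patient.

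**The titrator may have been blinded.** A reader might infer from the blinding sentence that the titrator knew the allocation, or that the sparing effect comes from titration. The documents support neither. They do not say who titrated, a separate person kept out of the room during the block is compatible with the text, and nothing shows that choices followed the arm. The defect is that the role producing the primary outcome is not covered.

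**Conclusion.** The point holds as a gap in protection and description, not as evidence of bias. Blinding is stated for participants and the outcome assessor but not for the titrator, and the SPI rule narrows arm-linked discretion without closing it.

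The size is conditional on assumed SPI behavior. It is about 0.25–0.4 µg/kg/h (6–7% rejection) for a start gap, a one-sided delay or delays in half the patients. It is about 0.8–1.3 µg/kg/h (13–29%) only for near-systematic opposite delays. Those are medians, and the ranges are wide. Even the largest simulated false difference, 2.48, is below the planned 3.6, so the results do not support a reading that titration alone would account for an effect of the planned size. Nor do they support saying that the planned analyses could not notice: the SPI comparison would often, but not always, reveal the larger scenarios.

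This is a worthwhile, cheap improvement; it does not invalidate the trial.

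**What to change.** **Design.** Add the titrator to the blinding sentence. The plan already gives the blocks to one anesthesiologist. Where staffing allows, use that separation so that the titrator is away during the block or no-block step. Give both arms the same dressing over the site and the same 15-minute wait before incision, and start both from one common remifentanil target chosen by the sponsor's clinicians. The SPI rule can stay as it is. No sham injection is needed.

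**Reporting, in any case.** From the pump and monitor records, report by arm the target at incision, the time from SPI leaving 20–50 to the next step, and mean SPI. Interpret the consumption difference alongside the planned SPI comparison. A nonsignificant SPI result should not be taken as proof that titration was even-handed. State who titrated and, if that person knew the allocation, list it as a limitation. The document gives primary completion as December 30, 2018, so for this trial only the reporting part can still be acted on.

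**Cost.** A brief handover during anesthesia, a 15-minute wait for controls, a dressing, and a little more analysis. No additional provider should be required; where existing staff cannot be separated, the reporting and limitation statement suffice. The surgeon may notice injectate and should be asked not to comment. No extra patients are needed: in the same model, with a true effect of about 3.6, power with a blinded titrator free to choose starts and intervals is 94% (90–96%), against 95% (94–96%) with fixed one-minute steps.

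### Does the lack of a rule for pain scores taken after rescue fentanyl undermine the 1 h comparison?

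*Combined protocol and SAP*

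**What the plan says.** All of this is in the combined protocol and SAP, which has no numbered sections.

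- **Postoperative assessment paragraph.** The numerical rating scale (NRS) "was accessed immediately after arrival at the PACU, 1 h postoperatively, 16–24 h postoperatively, and 24–48 h postoperatively". A fentanyl "bolus was administered as a rescue analgesic agent when the NRS was greater than 5 points". The trigger is the same in both arms. The paragraph does not say when rescue was given or whether its time was recorded.
- **Patient-controlled analgesia paragraph.** All patients have background analgesia for 48 h ("basal infusion rate 2 mL/h, 0.5 mL intermittent bolus with a 15 min lock-out interval").
- **Outcomes paragraph.** Remifentanil consumption is primary; "the secondary outcomes were the postoperative pain score and rescue analgesic requirement".
- **Statistical analysis paragraph.** For pain, the Mann–Whitney "Test was used for variables with a non-normal distribution (postoperative pain scores"). Rescue is tested separately: the chi-squared or Fisher's exact test was "used to analyze the categorical data (the use of atropine, ephedrine and rescue analgesics), where appropriate".
- **Header and closing line.** "Document date : June 16, 2019" and "Primary completion date : December 30, 2018".

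No sentence says whether a score that follows rescue is kept, replaced, excluded or merged with rescue use.

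**The concern.** The rescue trigger is itself a pain score, and the first scheduled score comes before the second. If the block works, more controls than block patients should exceed 5 on arrival and receive fentanyl. If that dose still acts at the 1 h score, it lowers the control arm's scores more than the block arm's, and the observed difference shrinks. A null 1 h result could then be taken to mean no early analgesic benefit, when part of the control arm's low score came from fentanyl.

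Only the 1 h score is in question. The arrival score precedes any rescue in recovery, and intraoperative remifentanil is complete before rescue can occur.

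**Working it through.** **What the plan supplies.** It gives the trigger, the assessment times, the tests and 20 patients per arm. It gives no mean, SD, rescue rate or fentanyl effect for pain. Its one sample-size figure (14 per arm, raised to 20) concerns remifentanil, so there is no stated figure for pain to reproduce.

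**Direction and size of the shrinkage.** Let *p_C* and *p_P* be the proportions rescued before the 1 h score in the control and block arms, and *e* the points by which fentanyl lowers that score. Ignoring the ends of the scale:

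observed difference ≈ no-rescue difference − *e* × (*p_C* − *p_P*)

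With an assumed 50% versus 23% rescued and a no-rescue difference of 1.48:

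- *e* = 1: 1.48 − 1 × 0.27 = 1.21 (simulated 1.21)
- *e* = 2: 1.48 − 2 × 0.27 = 0.94 (simulated 0.94)
- *e* = 3: 1.48 − 3 × 0.27 = 0.67 (simulated 0.66)

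With 11% versus 2%, the shrinkage at *e* = 1 is 1 × 0.09 = 0.09 points. It is zero if rescue rates are equal, or if nobody scores above 5 on arrival.

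**Power of the raw 1 h test.** The simulation used 20,000 trials per cell, 20 per arm, normal scores rounded and clipped to 0–10, SD 2, a difference of 1.5 before rounding and clipping, and arrival-to-1 h correlation 0.7. Rescue followed an arrival score above 5. All these inputs except the arm size and the trigger are assumptions.

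| Means, control / block | Rescued | No fentanyl effect | 0.5 point | 1 point | 2 points | 3 points |
|---|---|---|---|---|---|---|
| 5.5 / 4.0 | 50% vs 23% | 0.60 | 0.570 | 0.517 | 0.374 | 0.207 |
| 4.5 / 3.0 | 31% vs 10% | 0.60 | 0.579 | 0.539 | 0.448 | 0.309 |
| 4.0 / 2.5 | 23% vs 7% | 0.60 | 0.584 | 0.562 | 0.479 | 0.379 |
| 3.0 / 1.5 | 11% vs 2% | 0.59 | 0.587 | 0.573 | 0.547 | 0.491 |

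If the dose acts at 1 h in only half of those rescued, the losses are about 1–5, 3–13 and 5–24 percentage points for effects of 1, 2 and 3 points.

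**Validity.** With no block effect, the raw test rejects in 0.046–0.049 of trials. Rescue does not inflate its type I error.

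**What the other planned tests show.** Power is 0.59–0.61 for the arrival score and 0.03–0.33 for Fisher's test of rescue. When the raw 1 h test is null, one of these two is significant in 35–60% of trials (effects of 1–3 points). The share of trials in which all three are null moves little:

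- 5.5 / 4.0, 3 points: 0.314 against 0.259 without a fentanyl effect, a rise of 5.5 percentage points.
- 3.0 / 1.5, 1 point: 0.276 against 0.275, a rise of 0.1.
- 5.5 / 4.0, 3 points, correlation 0.4: 0.305 against 0.204, a rise of 10.1.

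**What an extra analysis would add.** The obvious candidate gives the worst rank to patients rescued before 1 h. Its power stays at 0.58–0.62 whatever the fentanyl effect. Where it is significant and the raw test is not, the arrival or rescue test is already significant in about 59–90% of those trials. In 2–10% of trials it is null when the raw test is positive.

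**The case for a change.** The strongest case for a change is that the protection works only if the 1 h score, the arrival score and rescue use are read together, and the plan does not say to do so. Rescue use alone is a weak safeguard at this size, since Fisher power never exceeds 0.33 in these scenarios. One interpretive sentence and one supplementary rank analysis would need no new patients or assessments, and an arrival score above 5 could stand in for rescue if times were not recorded.

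Part of this stands. The plan does not name what the 1 h comparison measures, the direction of the shrinkage is right, and a careless reader could misread a null 1 h result.

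The rest does not carry a change. The shrinkage is measured against pain without rescue, a target the plan never sets. The worst-rank composite does not estimate that target either. It mixes pain with an outcome already tested separately, and its fallback reuses the arrival score. The document also postdates primary completion, so an analysis added now would be post hoc unless it had been set beforehand, and it would rely on rescue times that may not exist.

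**Conclusion.** No change to the plan follows. With no exclusion or replacement rule, a Mann–Whitney test of pain scores means the scores as recorded, and an analyst would run it that way. This is a sound comparison of pain under care as delivered. The information that would expose a rescue effect is already collected and tested: arrival pain before rescue in recovery, and rescue use as a secondary outcome in its own right. Reading a null 1 h score beside those two results is ordinary interpretation.

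The possible loss of 1 h power runs from about 1 to 39 percentage points at correlation 0.7, but this range is illustrative. The top end needs half of controls rescued on arrival, despite background analgesia in both arms, and a 3-point effect still present at 1 h. At 11% versus 2% rescued and a 1-point effect, the loss is about 2 points. The more relevant figure is the added chance of missing the signal on all three results. That is 0 to 6 percentage points, or up to 10 at correlation 0.4. The conclusion rests on the as-observed reading and on reporting all the planned secondary results; it does not depend on any particular assumed rescue rate. The primary outcome and its sample size are unaffected.

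### Does the missing start, stop and unit for intraoperative remifentanil consumption leave the primary outcome undefined?

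*Combined protocol and SAP*

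**What the plan says.** The outcomes and sample-size paragraph defines the endpoint in one sentence: "The primary outcome was the intraoperative remifentanil consumption, and the secondary outcomes were the postoperative pain score and rescue analgesic requirement". No start event, stop event or unit is attached. Shortly afterwards the same paragraph puts numbers on the same term, from an earlier study: "The intraoperative remifentanil consumption was 10.9 2.9 g/kg/h and 7.3 3.3 g/kg/h in the control and Pecs groups, respectively" (the micro and plus-minus signs were lost when the PDF was read). The statistical analysis paragraph assigns the t-test to intraoperative dosages of remifentanil and propofol, again without a unit.

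Four other statements bear on timing:

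- The anaesthesia paragraph: "For anesthesia induction and maintenance, lidocaine (1 mg/kg), propofol, and remifentanil were administered". The drug is therefore running before incision in both arms.
- The block paragraph, for the Pecs arm only: "For the patients in the Pecs group, a linear ultrasound probe was placed on the lateral third of the clavicle".
- The next paragraph: "Fifteen minutes after the Pecs II block, a skin incision was made for the scheduled surgery". No time to incision is given for controls.
- The same paragraph ties titration by the Surgical Pleth Index (SPI) to the period during "the surgery, the remifentanil dose was adjusted to a target SPI of 20–50".

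**The concern.** Remifentanil consumption is the only primary endpoint, and a consumption rate depends on the interval over which it is taken. Incision to closure and induction to end of anaesthesia are different quantities. Before incision there is no surgical stimulus for the block to blunt, so counting that time could dilute a true effect.

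The more serious possibility is an imbalance. The plan describes a block and a 15-minute wait in one arm and nothing comparable in the other. The block probably followed induction: the order of the text suggests it, and so does "After the intervention, the participants and the investigator responsible for the study outcome assessment were blinded", since no sham is described. Remifentanil may then have been running through that wait. If the Pecs arm had more low-rate time in its denominator, its hourly rate would fall without any sparing effect. On a total-dose scale the extra infusion would push the other way. With neither the window nor the unit written into the definition, a reader could doubt which quantity was tested.

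**Working it through.** **Inputs from the plan.** Control 10.9 (SD 2.9), Pecs 7.3 (SD 3.3), per kg per hour; alpha 0.05, taken as two-sided; power 0.90; 14 per group required, 20 enrolled.

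**The plan's own figure.** Difference = 10.9 − 7.3 = 3.6. Pooled SD = √((2.9² + 3.3²)/2) = 3.106. The normal-approximation formula n = 2 × (1.960 + 1.282)² × SD² / 3.6² gives 15.6, so 16 per group. With the control SD of 2.9 it gives 13.6, so exactly the stated 14. The stated size is reproduced closely enough. By the noncentral t distribution, power with 20 per group is 94.6%. These calculations use the hourly per-kg scale, the only scale on which the plan quantifies this outcome.

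**Assumptions (not in the documents).** Surgery lasts S = 60 to 120 min; pre-incision time common to both arms is P = 15 or 30 min; E is any extra wait in the Pecs arm; q is a constant pre-incision rate, the same in both arms; 10.9 and 7.3 describe the surgical period.

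**Formula.** Whole-anaesthetic difference = (S × 10.9 + P × q)/(S + P) − (S × R + (P + E) × q)/(S + P + E), where R is the Pecs surgical rate.

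**1. Window is the surgical period.** P and E drop out and the difference is 3.6. Nothing shifts.

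**2. Whole anaesthetic, equal waits (E = 0, R = 7.3).** The q terms cancel and the difference is 3.6 × S/(S + P).

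| P (min) | S (min) | Factor | Difference | SD scaled by the same factor | Power, SD scaled | Power, SD held at 3.106 |
|---|---|---|---|---|---|---|
| 15 | 60 | 0.800 | 2.88 | 2.49 | 94.6% | 81.5% |
| 15 | 90 | 0.857 | 3.09 | 2.66 | 94.6% | 86.5% |
| 15 | 120 | 0.889 | 3.20 | 2.76 | 94.6% | 88.8% |
| 30 | 60 | 0.667 | 2.40 | 2.07 | 94.6% | 66.3% |
| 30 | 120 | 0.800 | 2.88 | 2.49 | 94.6% | 81.5% |

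With q and the times constant, a patient's whole-anaesthetic rate is the surgical rate times S/(S + P) plus a constant. The SD is therefore multiplied by the same factor as the difference, and the t-test is unaffected. The last column needs extra between-patient variation that this model does not contain.

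**3. No block effect (R = 10.9), with E = 15 and P = 15.**

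- q = 5.45 (half the surgical rate), S = 60: (654 + 81.75)/75 − (654 + 163.5)/90 = 9.810 − 9.083 = 0.727.
- q = 7.63 (70%), S = 120: 0.291.
- q = 14.17 (130%): −0.436 at S = 60 and −0.291 at S = 120.
- E = 0 or q = 10.9: exactly 0.

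For the 0.727 case, the rejection rate with 20 per group is 11.1% if the SD is held at 3.106 and 16.8% if it is scaled within each arm.

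**4. Wider assumptions.** With control pre-incision time of 5 to 15 min, a Pecs excess of 15 to 20 min and q from 2 to 15, the planned difference runs from 1.58 to 4.47 and the null difference from −0.89 to +1.93. The documents fix neither the size nor the sign of any shift.

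**The case for a change.** The strongest case for a change is that a sole primary endpoint should carry its start, stop and unit; that remifentanil runs from induction while SPI titration is described only for surgery; and that the wait is described in one arm only. The null shift in step 3 is not negligible if its conditions are met, and a sentence costs little.

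Part of this stands. The definition is thinner than it should be, and no adjective of size can be put on the effect of counting pre-incision time, because the plan gives none of the surgery time, the control wait or the pre-incision rate.

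The rest does not carry a change:

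- **Unit.** The same term is quantified per kg per hour within the same paragraph and the trial is sized on it. Dosages, in the analysis paragraph, is a loose word covering two drugs and does not set up a rival definition.
- **Window.** Intraoperative ordinarily means during the operation, and titration is described for that period.
- **Bias.** The null shift needs remifentanil running during the wait, a shorter wait in controls and a pre-incision rate unlike the surgical rate. The plan states none of these, and silence about control timing is not evidence of unequal timing.
- **Power.** The loss in the last column of the table comes from holding the SD fixed. It also assumes that the earlier study counted only the surgical period; if that study counted the whole anaesthetic, any dilution is already inside 3.6.
- **Preferred window.** A whole-anaesthetic rate is a legitimate quantity too, so insisting on incision to closure would be a preference.

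**Conclusion.** The gap is real but is one of missing detail. Analysts would fill it by taking the surgical period and the unit used for sample size, and on that reading the shift is zero. No rule in the plan is shown to give a wrong answer.

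Counting pre-incision time with equal waits of 15 minutes would give 2.88 to 3.20 in place of 3.6 (11% to 20% smaller) for surgery of 60 to 120 minutes. Under constant pre-incision rates and times, power would stay at 94.6%. A false difference arises only when both the waits and the rates differ, and the documents do not allow its size to be fixed.

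Primary completion was on December 30, 2018, so nothing in the trial's conduct can now be altered. Stating the window and unit used is a matter for the trial report, as is giving induction-to-incision time and pre-incision remifentanil by arm where recorded.

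### Is 14 patients per group wrong for 90% power, given that the plan does not state sidedness, SD or formula?

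*Combined protocol and SAP*

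**What the plan says.** The combined protocol and SAP has no section numbers; the relevant text is the sample-size paragraph and the statistical analysis paragraph after it.

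- Source of the planning values: "The sample size was calculated based on the previous study of breast cancer surgery under TIVA".
- The values: "The intraoperative remifentanil consumption was 10.9 2.9 g/kg/h and 7.3 3.3 g/kg/h in the control and Pecs groups, respectively". The plus-minus sign appears to have been lost when the PDF was read, so I take 2.9 and 3.3 to be SDs. That is an inference, though a natural one: the same loss occurs where the analysis paragraph describes how means and SDs are presented.
- The result: "With type 1 error of 0.05 and a power of 0.9, the study required 14 patients in each group".
- The margin: "Considering the possible drop-out, 20 patients were included in each group". No drop-out rate is given.
- The analysis: "An independent t-test was used for normally distributed variables (intraoperative dosages of remifentanil and propofol"), with the threshold "Statistical significance was accepted for p value < 0.05". No direction is stated.

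The file carries the line "Document date : June 16, 2019" and closes with "Primary completion date : December 30, 2018", so it was written after primary data collection ended.

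**The concern.** A sample-size statement should let a reader recover the number. Here the effect, the error rate and the target power are given, but three choices are not: one- or two-sided testing, which SD was entered, and whether the calculation used the t distribution or a normal approximation. Most statisticians would fill these gaps with a two-sided 5% t-test and an SD pooled over both arms. That calculation does not return 14; it returns 17, and 14 falls about six points short of the claimed power. Rounding in the printed means and SDs does not close the gap.

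Two things would be at stake. The stated 90% could be overstated. The increase from 14 to 20 per group, which reads as room for six losses per group, could in fact leave less room, with no assumed drop-out rate to judge it against.

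**Working it through.** **Inputs.** From the sample-size paragraph: control 10.9 (SD 2.9), Pecs 7.3 (SD 3.3), type 1 error 0.05, power 0.9, equal groups. The difference is 10.9 − 7.3 = 3.6. Candidate SDs are 2.9 (control), 3.3 (Pecs), and pooled √((2.9² + 3.3²)/2) = √((8.41 + 10.89)/2) = √9.65 = 3.106. Two-sided testing is my assumption wherever I use it.

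**Step 1: can 14 be reproduced?** The normal approximation per group is n = 2 × ((z_α + z_β) × SD / 3.6)², with z_β = 1.2816 for 90% power and z_α = 1.960 (two-sided) or 1.645 (one-sided).

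- Two-sided, SD 2.9: 2 × (3.2415 × 2.9 / 3.6)² = 13.64, rounded up to **14**.
- Two-sided, pooled SD: 2 × (3.2415 × 3.106 / 3.6)² = 15.65, rounded up to 16.
- Two-sided, SD 3.3: 17.66, rounded up to 18.
- One-sided, pooled SD: 12.75, rounded up to 13.

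With the exact t-test (noncentral t, 2n − 2 degrees of freedom, noncentrality 3.6 / (SD × √(2/n))), the one-sided 5% test with the pooled SD has power 89.0% at 13 and 91.0% at 14. The smallest sufficient n is again **14**.

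So two ordinary routes give exactly the printed number. The documents do not show which, if either, was used.

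**Step 2: exact two-sided 5% t-test, by choice of SD.**

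| SD | Power at 14 | Smallest n for 90% | Power at that n | Power at 20 | Losses per group that keep 90% |
|---|---|---|---|---|---|
| 2.9 (control) | 88.5% | 15 | 90.7% | 96.9% | 20 − 15 = 5 |
| 3.106 (pooled) | 83.9% | 17 | 90.6% | 94.6% | 20 − 17 = 3 |
| 3.3 (Pecs) | 79.3% | 19 | 90.5% | 91.9% | 20 − 19 = 1 |

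Simulation with the two unequal SDs agrees with the pooled row: 83.8% at 14, 90.6% at 17 and 94.6% at 20 for the equal-variance test, with the Welch test within about 0.2 points of it.

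**Step 3: rounding of the printed inputs.** Each mean and SD is moved by up to 0.05, two-sided.

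- Pooled SD: power at 14 runs from 80.6% to 86.9%, and the requirement from 16 to 19. Rounding does not rescue 14 on this reading.
- Pooled SD at 17 per group: 88.0% to 92.8%. The allowance of three losses therefore holds at the printed values and is not guaranteed beyond them.
- Pooled SD at 20 per group: 92.7% to 96.2%.
- Control SD: the requirement runs from 14 to 16, so on this route 14 lies within rounding even under the exact t-test.

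**Step 4: what was randomised.** The trial allocated 20 per group. Every two-sided SD choice in the table is above 90% at that size before losses. The increase from 14 to 20 corresponds to a loss of 1 − 14/20 = 30%. The pooled-SD margin, 20 down to 17, corresponds to 1 − 17/20 = 15%.

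**The case for a change.** The strongest case for acting is that neither route to 14 is disclosed and each needs something the plan does not say. The one-sided route needs a directional test, which is stated nowhere. The control-SD route sets aside the larger Pecs SD that the plan itself prints, and relies on a normal approximation although the named analysis is a t-test; the exact calculation with that same SD gives 88.5% and needs 15. A lone figure of 14 cannot be checked when defensible choices span 12 to 19 per group. Disclosure would cost a sentence or two, and sidedness also governs how the primary p-value is read.

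The omission is real, and a fuller paragraph would be better practice. What does not stand is the step from there to a wrong number. Using the control-arm SD and using a normal approximation are both planning conventions, and nothing in the text rules them out. The six-point shortfall belongs to one reading; on the two-sided reading that yields 14, it is 1.5 points and one patient per group. Nor should a review write in that the test is two-sided, since the documents do not say so; only the sponsor can report what was used. In a document dated after primary completion, that report would describe history and alter nothing still to be done. An analyst given an independent t-test, a 0.05 threshold and no direction would run it two-sided as a matter of course.

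**Conclusion.** The concern does not call for a change. The sidedness, the SD and the formula behind 14 are missing, but the number agrees exactly with two standard calculations, so it is not shown to be an arithmetic error. The statement that 14 gives 83.9% rather than 90% is correct only if the test is two-sided at 5% and both printed values are SDs that were pooled.

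On size: at the 20 per group randomised, two-sided power for the planned difference of 3.6 is 91.9% to 96.9% across SD choices before losses, so the 90% target is met. The one practical residue is the drop-out margin, which is 5, 3 or 1 per group with the control, pooled or Pecs SD, against the 6 implied by going from 14 to 20. These figures take the printed means and SDs at face value, and on the pooled reading power at three losses could fall to 88.0% from input rounding alone. This is a minor gap in reporting that leaves the design, the analysis and the conclusions unaffected.
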